1.2 OBJECTIVES

The objectives of this study are:

- To evaluate long-term safety and efficacy of caplacizumab
- To evaluate safety and efficacy of repeated use of caplacizumab
- To characterize long term impact of aTTP

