2.4.4.4.1 Presenting symptoms

The number and percentage of participants with presenting symptoms at the recurrence visit will be summarized for each recurrence episode. The denominator for the percentage calculation is the number of assessable participants at each time point.

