2.4.5 Analyses of safety data

The summary of safety results will be presented by treatment group. For the ITO population, the treatment groups are:

- Caplacizumab total: Subjects who received caplacizumab during the ALX0681-C301 study (during the double blind or the open-label periods).
- Not treated: Subjects who never received Caplacizumab during the ALX0681-C301 trial

For the recurrence population, adverse events will be presented for:

- Treated with IMP: patients treated with caplacizumab in the ALX0681-C302 study
- Not Treated with IMP: patients not treated with caplacizumab in the ALX0681-C302 study during the trial

General common rules

All safety analyses will be performed on the ITO and recurrence populations as defined in [Section 2.3.2](#), unless otherwise specified, using the following common rules:

- For analysis related to the Q6M FU visits, the baseline value is defined as screening/baseline value visit. For analysis related to the recurrence period, the baseline value is defined as the recurrence visit value and will be calculated for each recurrence period separately
- For assessments with multiple parameters per participant (such as laboratory assessments), baseline will be determined per parameter individually. It is recognized that baseline assessments may thus come from more than one assessment and not just from the “baseline visit” assessment.
- For quantitative safety parameters based on central laboratory/reading measurements, descriptive statistics will be used to summarize results and change from baseline values by visit.
- The analysis of the safety variables will be essentially descriptive, and no systematic testing is planned.

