2.4.5.1 Analyses of adverse events

Generalities

The primary focus of adverse event reporting will be on treatment-emergent adverse events. Pretreatment and posttreatment adverse events will be described separately.

If an adverse event date/time of onset (occurrence, worsening, or becoming serious) is incomplete, an imputation algorithm will be used to classify the adverse event as pretreatment,

treatment-emergent, or posttreatment. The algorithm for imputing date/time of onset will be conservative and will classify an adverse event as treatment emergent unless there is definitive information to determine it is pretreatment or posttreatment. Details on classification of adverse events with missing or partial onset dates are provided in [Section 2.5.3](#).

Adverse events (AEs) will be placed into analysis periods according to their start date (time). The AE will only be presented in the analysis period during which it started, ie, period start date (time) \leq AE start date (time) \leq period stop date (time). There will be no imputation of other missing date (time) fields, nor of the missing parts of other partially known date (time) fields. When needed (e.g., an incomplete date (time) leads to a double phase allocation), the following rules will be applied: adverse events will be allocated on all analysis levels (ie, for analysis periods and subperiods, see [Section 2.5.4](#)) according to their start date (time). In case the adverse event (AE) start date(time) is incomplete, the allocation will be done according to the available parts of the AE start date(time) and taking into account the AE end date(time) (ie, the AE start date(time) cannot be later than the AE end date(time)):

- When, due to missing date (part) an allocation needs to be made to an analysis period, the AE will be allocated to the treatment phase and not off-treatment phase (worst-case allocation).
- When an allocation needs to be made to a specific recurrence period, the AE will be allocated to the first recurrence period.
- When an allocation needs to be made within a recurrence period, the event will be allocated to the daily PE subperiod.

Tables on the recurrence population will include only adverse events that occurred during the recurrence period, treatment-emergent (for patients who received the IMP) and non-treatment emergent (for patients who did not received the IMP).

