When cross-tabulating AE PTs versus an AE attribute (e.g., severity), the worst-case is always applied within each analysis period. This means that when a participant has the same AE PT twice in the same analysis period, then the participant is reported only once: with the worst severity. If this happens in two different analysis periods, the participant is reported twice: once in each analysis period.

AE onset day and AE duration are defined as follows:

- AE onset day
 - AE start date – reference date + 1 day (when the AE start date is completely known)
 - Missing (when the AE start date is incomplete or unknown).
 - Two different onset days will be calculated: one with the reference date being the screening/baseline visit; and the other, for adverse events occurring during the recurrence period, with reference date being the recurrence visit.
- AE duration
 - AE stop date – AE start date + 1 day (when both dates are completely known)

- Trial termination date – AE start date + 1 day (when the AE start date is fully known but the AE is not resolved at the end of the trial): in this case the duration will be presented as “>x days” in the listing rather than “x days”
- Missing (when the AE start date is incomplete or unknown, or when the AE has resolved but with an incomplete or unknown end date).

These derived parameters will only be presented in the listings. Note that the start and stop times of the AE are not used.

AE incidence tables will present by SOC and PT, sorted by decreasing frequency of SOC and PTs within SOCs, the number (n) and percentage (%) of participants experiencing an adverse event. The denominator for computation of percentages is the population within each treatment group.

The following analysis periods will be considered for all TEAEs tables on the recurrence population:

- Treatment daily PE period
- Treatment post-daily PE period
- Overall treatment period
- Follow-up period
- Overall recurrence period

The following analysis periods will be considered for AE occurring in the recurrence periods for patients not treated with the IMP:

- Daily PE period
- Post Daily PE period
- Overall recurrence period

The following analysis period will be considered for the adverse events observed during the study for the ITO population:

- Overall study period

Analysis of all adverse events

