2.5.4 Windows for time points

The following analysis periods and phase are defined for this study for the Q6M FU visits and the recurrence period.

Table 1 – Analysis phases and periods for the recurrence period- Caplacizumab treated patients

Phase	Period	Subperiod	Start date	End date
Recurrence episode x	Treatment	Daily PE	Recurrence visit date of the recurrence episode	End date of the daily plasma exchange in the recurrence episode
		Post-daily PE	End date of daily plasma exchange in the recurrence episode + 1 day	End date of the treatment period in the recurrence episode
	Follow-up		End date of treatment period + 1 day	Recurrence follow-up visit date

Table 2 – Analysis phases periods for the recurrence period – non-treated patients

Phase	Period	Subperiod	Start date	End date
Recurrence episode x	No-treatment	Daily PE	Recurrence visit date in the recurrence episode	End date of daily plasma exchange in the recurrence episode
	Follow-up		End of daily plasma exchange in the recurrence episode + 1 day	Recurrence follow-up visit date

Table 3 – Analysis phases and periods for the Q6M FU visits

Phase	Period	Subperiod	Start period	End period
Observation			Screening/baseline visit	End of participation to the trial

Note that the last analysis period in case of early termination will always be ended by the trial termination date.

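### AE percentages by analysis period are divided by the whole treatment group, so they are understated for any period or episode that not every participant enters

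*SAP*

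**What the plan says.** SAP 2.4.5.1 (Analyses of adverse events) states for the AE incidence tables: "The denominator for computation of percentages is the population within each treatment group". It gives no other AE denominator. For treated patients in the recurrence population, it then lists the periods to be tabulated: daily PE, post-daily PE, overall treatment, follow-up and overall recurrence.

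SAP 2.4.5 defines the treated group for these tables as "Treated with IMP: patients treated with caplacizumab in the ALX0681-C302 study". Membership is for the study as a whole, not for a given episode.

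SAP 2.5.4, Table 1, places the treatment and follow-up periods inside a phase labelled "Recurrence episode x".

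For incomplete AE start dates that the available date parts and the end date cannot resolve, SAP 2.4.5.1 says: "When an allocation needs to be made to a specific recurrence period, the AE will be allocated to the first recurrence period".

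Other parts of the SAP do it differently. Presenting symptoms use "The denominator for the percentage calculation is the number of assessable participants at each time point", and the sections on episode duration and outcome (2.4.4.4.2 and 2.4.4.4.3) repeat that rule. The immunogenicity groups (2.4.5.5.5) define treated and not treated separately for each recurrence episode.

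**The concern.** A percentage for a period should be read against the people who could have had an event in it. Participants drop out of that set in three ways: they die or withdraw during an earlier period; they recur while still on treatment and start a new cycle, so they never reach the follow-up of the first episode; or they never have a second episode. Under the stated rule all of them still count in the denominator.

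This matters because one of the three objectives is "To evaluate safety and efficacy of repeated use of caplacizumab" (SAP 1.2). No formal test is planned (SAP 2.4.4.8), so descriptive tables are the evidence. Protocol 3.6.1 leaves subsets by retreatment to the SAP, and SAP 2.4.5 defines none for AEs. If the tables are split by episode, later episodes carry the largest dilution. If they are pooled over episodes, no AE table isolates later episodes at all. Both readings leave something to correct.

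The partial-date rule adds a smaller effect in one direction: an unresolved AE can move out of a later episode but never into one.

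**Working it through.** The plan states no figure for this point, so there is nothing to reproduce. All counts below are assumptions chosen to show the mechanism; the documents give no numbers of treated participants, repeat episodes or partial dates.

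**Formula.** Let N be the treatment group, n the participants who entered the period or episode, and x those with the AE in it.

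Printed % = x/N = (x/n) × (n/N).

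The dilution factor is n/N.

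**Post-daily PE, nearly everyone enters.** N = 30, n = 28, x = 6: printed 6/30 = 20.0%; among those who entered 6/28 = 21.4%.

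**Second treated episode, a minority enters.** N = 30, n = 10, x = 4: printed 4/30 = 13.3%; among those who entered 4/10 = 40.0%, a factor of 3.

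**Range.** With N = 30 and 30% expected among those who entered:

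| n entering | 28 | 24 | 15 | 9 | 6 | 3 |
|---|---|---|---|---|---|---|
| Printed % (0.30 × n/30) | 28 | 24 | 15 | 9 | 6 | 3 |

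**Person-month rate in the overview tables.** SAP 2.4.5.1 defines it as 100 × participants with an AE / months observed within the period. Take 15 of 30 with an AE in episode 1, 4 of 10 in episode 2, and 1.5 months per episode:

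- Episode 1: 100 × 15/(30 × 1.5) = 33.3
- Episode 2: 100 × 4/(10 × 1.5) = 26.7
- Ratio of later to first: 26.7/33.3 = 0.80

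At 1.2 months the rates are 41.7 and 33.3, and at 2.5 months 20.0 and 16.0; the ratio stays 0.80. It equals the ratio of percentages among those who entered, 40%/50% = 0.80. The whole-group percentages give 13.3%/50% = 0.27. An overview table split by episode would thus print a diluted percentage beside an undiluted rate.

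**Partial dates.** Suppose 1 or 2 of the 4 participants with an episode-2 AE have only an unresolved date, and their AE moves to episode 1. The whole-group figure falls from 13.3% to 3/30 = 10.0% or 2/30 = 6.7%. With the corrected denominator it falls from 40.0% to 3/10 = 30.0% or 2/10 = 20.0%. Correcting the denominator does not remove this effect, so it needs its own check.

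**The case against.** The strongest reply is that the SAP never commits to AE percentages by episode number. The period list in 2.4.5.1 carries no episode split, whereas other sections (for example 2.4.1 and 2.4.4.4.1) say so when they want one. This stands. By-episode AE tables are implied only by the phase label in Table 1 and by the allocation rule, which would have little purpose if episodes were pooled. The several-fold dilution is therefore conditional; the dilution by period is not.

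The second reply is that the overview tables give person-month incidence, which is free of the dilution and covers any AE, serious AEs, deaths, bleeding, thromboembolic events and, for TEAEs, hypersensitivity. Many detailed tables also give event counts, and participants per period are tabulated under SAP 2.2. This also stands, as mitigation. The SOC/PT and severity tables still have no such rate, and a reader would have to rebuild each percentage by hand.

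A reader might go further and infer that the plan makes repeated use look safer than first use. The documents do not support that in general. Anyone given caplacizumab in C301 is already re-exposed at the first C302 recurrence, so moving an AE to that episode keeps it within repeated use. The clear distortion is between later and first C302 episodes. Nor is the first-recurrence rule presented as worst-case: that label belongs to the bullet before it, on treatment versus off-treatment, which is conservative.

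**Conclusion.** The stated denominator is wrong for any table by period that some of the group did not enter. The understatement is exactly n/N: probably minor for post-daily PE, where most participants are likely to enter, and potentially several-fold for a second or later episode if tables are split that way. The direction follows from the text alone; the size does not, because no C302 counts are given.

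It is tempting to take n/N from the Phase II study, where 13 of 36 caplacizumab subjects (36.1%) had an exacerbation and/or relapse (Protocol 1.2.4). That is the share recurring after a presenting episode, not the share of C302 recurrence subjects who have a second treated episode, so it does not fix the size here.

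The denominator is the essential correction. The partial-date rule is secondary: it applies only when the date parts and end date leave the episode open, and its effect cannot be quantified from the documents.

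**What to change.** 1. Replace the denominator sentence in SAP 2.4.5.1 with: *The denominator is the number of participants in the group who entered that analysis period (and, where tables are by episode, that recurrence episode), printed in each column header.*
2. State that TEAE tables are presented by recurrence episode, and define treated and not treated per episode, as SAP 2.4.5.5.5 already does for immunogenicity.
3. Keep the first-recurrence rule for partial dates, but report how many AEs it decided and add a sensitivity table that allocates them to the latest compatible treated episode. Making that the main rule would only swap one arbitrary choice for its opposite.

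The cost is a few sentences and one extra table; SAP 2.2 already plans the counts by period and subperiod. Percentages for later periods will be less favourable and, with small denominators, less precise.

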The efficacy and safety of caplacizumab in the treatment of acquired TTP have been evaluated in Study ALX-0681-2.1/10 comparing it to placebo when added to daily PE and in the 30-day post-daily PE period [16]. The study was terminated early due to recruitment challenges, with a total of 75 subjects enrolled and included in the intention-to-treat (ITT) analysis. The primary endpoint was the time to confirmed normalization of the platelet count. The median time to confirmed response was 2.97 days in the caplacizumab treatment group and 4.79 days in the placebo group. Based on the stratified log-rank test, the time to response was significantly shorter in the caplacizumab treatment group, compared with the placebo treatment group ($p=0.005$), taking into account presence or absence of one PE session prior to randomization. This is also demonstrated by a hazard (i.e., event rate) ratio (95% confidence interval) for the caplacizumab versus placebo treatment groups of 2.197 (1.278, 3.778).

The secondary endpoints illustrate the potential protective effect of caplacizumab treatment in the acute phase of TTP.

- A substantially higher number and proportion of subjects in the caplacizumab treatment group achieved complete remission following the initial course of daily PE compared with subjects in the placebo treatment group (29 [80.6%] subjects versus 18 [46.2%] subjects, respectively).
- Fewer subjects in the caplacizumab treatment group had exacerbations of TTP compared with the placebo treatment group (3 [8.4%] and 11 [28.2%] subjects, respectively).
- A similar number and proportion of subjects in the caplacizumab treatment group and the placebo treatment group had an exacerbation and/or a relapse of TTP (13 [36.1%] and 13 [33.3%] subjects, respectively). This suggests that in a number of subjects, the underlying auto-immune activity had not sufficiently resolved. Immunosuppressive treatment was not standardized and the shorter duration of PE in the caplacizumab arm may also have impacted the timing of the resolution of the underlying auto-immune disorder.
- The mean number of PE days during the initial daily PE period was lower in the caplacizumab group compared with the placebo group (5.9 versus 7.9, respectively), as was the mean total volume of PE administered (19923 mL versus 28307 mL, respectively).

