A total of 574 TEAEs were reported in 34 (97.1%) subjects in the caplacizumab treatment group compared with 545 TEAEs in 37 (100%) subjects in the placebo treatment group. No subjects in the caplacizumab treatment group died during the study. Two subjects in the placebo treatment group died between the end of study treatment up to and including 1 month FU: one subject had a treatment emergent adverse event (TEAE) of cerebral hemorrhage which was assessed as related to TTP; the other died from the serious TEAE of refractory TTP. Serious adverse events (SAEs) were reported in a similar number of subjects in the two treatment arms (57.1% in the caplacizumab group and 51.4% in the placebo group). The number of subjects with any TEAE leading to discontinuation of study drug was 4 and 2 in the caplacizumab and placebo groups, respectively.

The occurrence of treatment-emergent major thromboembolic adverse events was investigated in the clinical study database, using the Standardized MedDRA Query for 'embolic and thrombotic events'. The proportion of subjects with at least one of these events together with the total number of events were summarized and reported per treatment group. Transient episodes were not considered major thromboembolic events and

were, therefore, not included in this analysis. TTP-related mortality during the study was evaluated based on AE reporting, with relatedness to TTP as judged by the Investigator. The safety population consisted of 35 caplacizumab-treated and 37 placebo-treated subjects. Four major thromboembolic events were reported in 4 subjects in the caplacizumab group (1 pulmonary embolism and 3 TTP exacerbations). In the placebo group, 20 major thromboembolic events were reported in 14 subjects (2 acute myocardial infarctions, 1 ischemic and 1 hemorrhagic stroke, 1 pulmonary embolism, 1 deep vein thrombosis, 1 venous thrombosis and 13 TTP exacerbations). Two TTP-related deaths occurred during the study, both in the placebo treatment group (causes of death: refractory TTP and cerebral hemorrhage). In total, 11.4% of caplacizumab-treated subjects versus 43.2% of placebo-treated subjects experienced one or more thromboembolic events or died. The results of this analysis suggest that treatment with caplacizumab has the potential to reduce the significant morbidity and mortality associated with acquired TTP.

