The proportion of subjects with any bleeding-related TEAE was higher in the caplacizumab treatment group (54.3% of subjects) than in the placebo treatment group (37.8% of subjects); most bleeding-related TEAEs were mild (83% of events) or moderate (14% of events) in severity. Amongst the bleeding-related TEAE, epistaxis was the most common Preferred Term (31% of subjects for ALX-0081 and 11% of subjects for placebo [all mild or moderate]). Two subjects in each treatment arm experienced serious bleeding related TEAEs. The TE bleeding AEs did not lead to emergency measures. Furthermore, no vWF or Factor VIII supplementation was administered during the study.

Treatment-emergent anti-drug antibodies (ADA) were detected in 9% of the subjects in the ALX-0081 treated group and in no placebo treated subjects. These had no apparent influence on PK and PD parameters. There was also no association found between the ADAs and safety findings.

Study ALX-0081-2.1/09

This study evaluated caplacizumab in patients undergoing a percutaneous coronary intervention. Caplacizumab was given as a 6 mg i.v. injection prior to the intervention and with 4 mg i.v. injections every 6 hours afterwards for 3 doses. The primary endpoint of the study was a composite of all bleeding events according to the Thrombolysis in Myocardial Infarction (TIMI) classification and was designed to detect a relative risk reduction of 0.4 (caplacizumab versus abciximab [ReoPro®]). Both caplacizumab and abciximab showed similar bleeding profiles: 36 (19.9%) patients in the caplacizumab treatment group and 28 (15.3%) patients in the abciximab treatment group reported bleeding events. Three (1.7%) caplacizumab-treated patients and 2 (1.1%) abciximab-treated patients experienced a major bleeding event during the 30 day period following the PCI procedure. The safety profile of caplacizumab and abciximab was similar in this study. The proportion of SAEs was low in both treatment groups. Serious TEAEs were reported in 24 (13.3%)

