The following adverse event summaries will be generated by analysis period for the patients not treated in the recurrence population and for the ITO population.

- Overview of adverse events, summarizing number (%) of participants, the number of events, and the incidence per 100 person months, which will be calculated as: $100 \times (\text{Number of participants with AE}) / (\text{Total number of months observed within analysis period, summed for all participants})$ with any
 - Participants with at least one AE
 - Participants with at least one serious AE

- Participants with at least one AE leading to death
- Participants with at least one PE-related AE (only for the recurrence population)
- Participants with at least one serious PE-related AE (only for the recurrence population)
- Participants with at least one bleeding event, i.e. an event documented as event indicating an increased bleeding tendency
- Participants with at least one bleeding event, based on the Standardized MedDRA Query (SMQ) “Haemorrhage” with exclusion of the PT “TTP”
- Participants with at least one thromboembolic event, based on the SMQ “Embolic and thrombotic events” (arterial, venous, and vessel type unspecified and mixed arterial and venous) with exclusion of the PT “TTP”
- All AE by primary SOC and PT, showing the number (%) of participants with at least 1 AE. The number of events and the number and percentage of participants having an event will be presented.
- AEs will be summarized by SOC, PT and severity. This will be done for each analysis period. The number and percentage of participants having an event will be presented for the worst severity reported for each event.

Analysis of all treatment-emergent adverse events

The following treatment-emergent adverse event summaries will be generated by analysis period for the recurrence population.

- Overview of treatment-emergent adverse events, summarizing number (%) of participants, the number of events, and the incidence per 100 person months, which will be calculated as: $100 \times (\text{Number of participants with AE}) / (\text{Total number of months observed within analysis period, summed for all participants})$ with any
 - Participants with at least one TEAE
 - Participants with at least one serious TEAE
 - Participants with at least one TEAE leading to death
 - Participants with at least one TEAE for which the study drug was interrupted
 - Participants with at least one TEAE for which the study drug was withdrawn

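### The adverse event incidence per 100 person-months counts each participant once but keeps their time after the first event, so it understates the rate for common events and depends on period length

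*SAP*

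**What the plan says.** SAP 2.4.5.1 defines two overview tables. One covers all adverse events (ITO population, and untreated recurrences); the other covers treatment-emergent events in the recurrence population. Each shows the number and percentage of participants, the number of events, and "the incidence per 100 person months, which will be calculated as" 100 times the number of participants with the event over the "Total number of months observed within analysis period, summed for all participants". The formula is the same in both tables and for every row. No rule in the SAP ends a participant's time at the first event, and SAP 2.2 derives period duration as end date minus start date plus one day.

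The rate is produced by analysis period. The sentence beginning "The following analysis periods will be considered for all TEAEs tables on the recurrence population" introduces the daily PE, post-daily PE, overall treatment, follow-up and overall recurrence periods. For the ITO population the period is the whole study, about 3 years per participant.

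Two date rules in the same section bear on any correction. The AE onset day is "Missing (when the AE start date is incomplete or unknown"), and for partly dated events the SAP states: "When an allocation needs to be made within a recurrence period, the event will be allocated to the daily PE subperiod".

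**The concern.** The usual reason for a person-time rate is to compare groups or periods that were watched for different lengths of time. A first-event rate does this by dividing participants with an event by the time until that event. An event rate does it by dividing all events by all time. The SAP takes the numerator of the first and the denominator of the second. Time after a first event can only enlarge the denominator, so the value is too low as a first-event rate, and the shortfall grows with the proportion affected and with the length of the period.

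Period lengths differ by design. Daily PE lasts days and post-daily PE treatment lasts 30 days, extendable by up to 28. A treated recurrence ends at a visit 7 days after the last caplacizumab dose, and an untreated one 30 days after daily PE. At one underlying rate, the longer period shows the lower figure. Bleeding is the main known safety finding for this drug (Protocol 1.2.5), and safety of repeated use is a study objective. A low rate in long or extended treatment periods could be read as reassurance when the formula produced it.

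**Working it through.** The documents state no adverse event rate for this study, so there is no planned figure to reproduce. The check uses algebra plus an illustration.

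**Inputs from the documents**
- Phase II proportions, Protocol 1.2.4: "A total of 574 TEAEs were reported in 34 (97.1%) subjects in the caplacizumab treatment group" (34/35); bleeding "higher in the caplacizumab treatment group (54.3% of subjects) than in the placebo treatment group (37.8% of subjects") (19/35 and 14/37).
- Phase II mean daily PE days, Protocol 1.2.4: "lower in the caplacizumab group compared with the placebo group (5.9 versus 7.9, respectively").
- 30 days of post-daily PE treatment, an extension of at most 28 days, and follow-up visits at 7 days (treated) or 30 days (untreated).

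**Assumptions**
- Constant first-event hazard h per month and equal follow-up of m months; one month is 30.4375 days.
- The Phase II proportions accrued over 5.9 + 30 = 35.9 days. The documents do not state that window, so it is varied below.
- The Phase II PE durations apply to treated (5.9) and untreated (7.9) recurrences.

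**Formulas**
- p = 1 - exp(-hm)
- SAP value = 100p/m
- Time-at-risk rate = 100h = 100 × (-ln(1-p))/m
- Ratio of the two = p/(-ln(1-p)), which depends only on p
- Ceiling of the SAP value = 100/m

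**Step 1: understatement by row**

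| Row (Phase II proportion) | p | -ln(1-p) | SAP value / time-at-risk rate |
|---|---|---|---|
| Any TEAE, caplacizumab | 0.971 | 3.540 | 0.27 |
| Serious AE, caplacizumab | 0.571 | 0.846 | 0.67 |
| Bleeding, caplacizumab | 0.543 | 0.783 | 0.69 |
| Bleeding, placebo | 0.378 | 0.475 | 0.80 |
| Serious bleeding, 2/35 | 0.057 | 0.059 | 0.97 |

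The bleeding ratio between groups is 0.783/0.475 = 1.65 on time at risk and 0.543/0.378 = 1.44 on the SAP formula.

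**Step 2: the same hazard in periods of different length**

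For bleeding, h = 0.783/(35.9/30.4375) = 0.664 per month. For any TEAE, h = 3.540/(35.9/30.4375) = 3.002 per month. The time-at-risk rates are therefore 66 and 300 per 100 person-months in every period.

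| Period | Days | Months | Ceiling | SAP, bleeding | SAP, any TEAE |
|---|---|---|---|---|---|
| Daily PE | 5.9 | 0.194 | 516 | 62 | 228 |
| Post-daily PE | 30 | 0.986 | 101 | 49 | 96 |
| Treated recurrence (5.9 + 30 + 7) | 42.9 | 1.409 | 71 | 43 | 70 |
| Treated, full extension (+ 28) | 70.9 | 2.329 | 43 | 34 | 43 |
| Untreated recurrence (7.9 + 30) | 37.9 | 1.245 | 80 | 45 | 78 |

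The daily PE to post-daily PE ratio, truly 1, appears as 1.28 for bleeding and 2.4 for any TEAE. For a row with p = 5% over 35.9 days, both periods show 4.3 and the ratio is 1.02. A simulation of 1,000,000 exponential event times at h = 0.664 gave SAP values of 62.4, 48.8, 43.1, 33.8 and 45.2, and time-at-risk rates of 66.4 to 66.5 in all five periods.

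**Step 3: sensitivity to the Phase II window**

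If the proportions accrued over 65.9 days (30 days longer), the daily PE to post-daily PE ratio is 1.15 for bleeding and 1.7 for any TEAE. Bleeding over the whole recurrence is then 28.3 treated and 29.1 untreated.

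**Step 4: ITO population over 36 months**

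The ceiling is 100/36 = 2.8 per 100 person-months. Assumed hazards of 0.1, 0.01 and 0.001 per month give SAP values of 2.70, 0.84 and 0.098 against true rates of 10, 1.0 and 0.10.

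**The case against.** The SAP states numerator and denominator openly and never calls the result a first-event rate, so this can be seen as a loosely labelled summary. The same row shows participants and events. Where at least one participant is affected, person-months can be recovered as 100n divided by the incidence, and the event rate follows. No tests are planned. Nothing is lost from the data, and that stands. But a reader takes a column labelled as incidence per person-time at face value, and the percentage beside it makes no adjustment for time.

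Treated and untreated recurrences appear in separate overviews. The untreated group is selected mainly by the treatment criteria, so no rate formula makes that comparison causal. The unextended bleeding difference is only 43 against 45, and the 34 needs every treated recurrence to use the full extension, for which the documents give no frequency. These points stand, and they make the contrast between subperiods the stronger illustration. The unstated Phase II window also stands; the longer window reduces the distortion without removing it.

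A time-at-risk rate does not remove all dependence on period length either. With assumed hazards of 2.0 per month during 5.9 PE days and 0.3 afterwards, it is 62 over 42.9 days and 52 over 70.9 days. The SAP formula gives 38 and 28 for the same hazards, so the dependence is larger and the level well below.

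Finally, onset is handled in whole days, so for near-universal rows in a PE period of about 6 days the corrected denominator is sensitive to the day-counting convention. That is a reason to show person-months and the event rate beside it.

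**Conclusion.** The concern holds. The direction needs no model, because time after a first event can only enlarge the denominator. The size rests on constant hazard, equal follow-up and Phase II proportions used as illustration; this study's own proportions are not in the documents. On those assumptions the column shows about a quarter of the first-event rate for any treatment-emergent event and 70 to 80% of it for bleeding. It can also create differences between periods of 1.15 to 1.28 for bleeding and 1.7 to 2.4 for any event where none exists. The serious adverse event row may be affected too, since every exacerbation and relapse must be reported as serious (Protocol 3.4.9.1). Rare rows, and rows where the event ends observation, are essentially correct. Because the analysis is descriptive and counts are shown, this is a misleading safety column that should be corrected, and it does not put the study's conclusions as a whole in doubt.

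**What to change.** In both overview tables of SAP 2.4.5.1:
- Replace the formula with 100 × (participants with at least one event of that row) / (sum of months from period start to the first event of that row, or to the end of observation in the period if there is none).
- Add a rule for incomplete onset dates, written as an exception to the general rule against imputing dates. Keep the event in the period to which the existing allocation rules assign it. Use the earliest date in that period consistent with the known date parts and the event's end date. Footnote how many participants this affects; the rule shortens person-time and so raises rates slightly.
- State how a first event on the first day of the period contributes time.
- Add 100 × (number of events) / (total months observed), labelled as an event rate, and show the person-months.

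The cost is row-specific denominators, the partial-date rule and reprogramming of two tables. No new data are needed. Reported rates for common events will rise. If only one change is possible, events over total months under a correct label is the cheaper partial remedy.
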